**Table 4 Dose Modification and Management Guidelines (cont.)**

Toxicity	Dose Modification and Management Guidelines
Vaginal or Uterine Hemorrhage:	
General	

Grade <math>\geq 2</math> vaginal or uterine hemorrhage is identified as an AESI requiring expedited reporting from study sites regardless of seriousness.

Prior to enrollment, screening scan of the uterus with transvaginal ultrasound must be performed. Due to the potential risks of changes in the female reproductive tract and uterotrophic effects, patients with a history of endometrial polyps, endometrial cancer, atypical endometrial hyperplasia, or other significant endometrial disorders should be excluded unless they have undergone total hysterectomy, and there is no evidence of active disease.

Grade 1	

Seek consultation with gynecologist or other specialist for differential diagnosis and appropriate management.

Transvaginal ultrasound should be considered.

Grade $\geq 2$	

As Grade 1.

Hold dosing with GDC-0810 until resolution to Grade <math>\leq 1</math>.

Discuss with study Medical Monitor for appropriate dose modification and management

Elevation of hepatic transaminases:	
General	

Patients presenting with jaundice, coagulopathy, abdominal pain, or other symptoms suggestive of hepatic pathology should have their liver function tests checked and imaging of the liver performed. If the liver enzymes are elevated with no obvious malignant cause found, a hepatologist should be consulted.

Patients experiencing hepatic enzyme elevation should be treated and managed per standard of care.

Grade $\geq 3$	

Hold study drug until resolution to baseline or below upper limit of normal (ULN).

AESI = adverse event of special interest.

#### **10.4.2 Dose Modifications for Phase Ib Cohort C1**

During the dose escalation DLT evaluation period, dose modifications will not be permitted; however, dose interruptions can be instituted for patient safety purposes. In Phase Ib Cohort C1, any grade non-hematologic toxicity assessed as related to GDC-0810 and/or palbociclib that leads to study drug interruption of  $> 7$  days' duration will meet the criteria for DLT. Patients who miss  $\geq 7$  doses of GDC-0810 or  $\geq 5$  doses of palbociclib during the DLT evaluation period due to reasons other than a DLT will be replaced.

After the DLT evaluation period is concluded, dose interruptions and/or reductions to the next lower dose level will be permitted as needed, provided that study discontinuation criteria have not been met (e.g., documented disease progression or unacceptable toxicity). Dose modification guidelines for treatment-related non-hematologic and hematologic toxicities are shown in [Table 5](#) and [Table 6](#), respectively.

GDC-0810 dose reductions may occur in decrements of 200 mg. Therefore, the possible GDC-0810 doses permitted in Phase Ib Cohorts C1 and C2 are 600 mg, 400 mg, and 200 mg. Because no more than two dose reductions are permitted, patients should discontinue GDC-0810 if they experience adverse events at 200 mg of GDC-0810 requiring dose reduction.

Palbociclib dose reductions may occur in decrements of 25 mg. Therefore, the possible palbociclib doses permitted in Phase Ib Cohorts C1, C2 and C3 are 125 mg, 100 mg, and 75 mg. Palbociclib dose de-escalation below 75 mg/day is not allowed, but in consultation with the sponsor, the schedule may be changed for example to 75 mg/day 2 weeks on followed by 2 weeks off (2/2 schedule).

Both GDC-0810 and palbociclib *must* be held in the presence of the following toxicities potentially attributed to the study drug:

- Decrease in post-treatment GFR of more than 25% as compared to baseline
- Any other Grade  $\geq 3$  non-hematologic adverse events potentially attributed to the study drug.

**Table 5 Dose Modification Guidelines for Treatment-Related Non-Hematologic Toxicities**

Toxicity	Palbociclib and/or GDC-0810 Dose Modification
Gastrointestinal Toxicities:	
General	

Patients should be closely monitored for gastrointestinal (GI) symptoms and their effects on their wellbeing. Patients experiencing nausea, vomiting, and diarrhea should be treated and managed per standard of care and per protocol guidelines, including use of anti-diarrheal agents and appropriate supportive care including hydration and dietary modification if clinically indicated.

Diarrhea:	
General and Grade 1	

See Section 10.4.1.

If diarrhea does not resolve after 14 days and GDC-0810 has already been held, consider withholding palbociclib.

If palbociclib hold was required, consider starting loperamide 2 mg 1–2 times daily as secondary prophylaxis (i.e., use of loperamide to prevent further diarrhea).

Grade 2 diarrhea	

See Section 10.4.1.

If diarrhea persists for more than 7 days after GDC-0810 is held, consider withholding palbociclib until symptoms resolve to Grade <math>\leq 1</math>.

If palbociclib hold was required, consider starting loperamide 2 mg 1–2 times daily as secondary prophylaxis (i.e., use of loperamide to prevent further diarrhea) upon restart.

Grade $\geq 3$ diarrhea	

Manage with adequate anti-diarrheal agents (e.g., loperamide) and maximum supportive care according to local standards and practices.

Closely monitor for resolution.

Withhold GDC-0810 and palbociclib until symptoms resolve to Grade <math>\leq 1</math>.

At resolution of first occurrence, reduce the dose of GDC-0810 by one dose level on improvement to Grade <math>\leq 1</math>. Consider reducing palbociclib by one dose level.

At resolution of second occurrence, reduce dose of GDC-0810 by one dose level on improvement to Grade <math>\leq 1</math>. Consider reducing palbociclib by one dose level.

On third occurrence, discontinue GDC-0810

At any occurrence of Grade 4 diarrhea, consider discontinuation of GDC-0810.

Upon resolution, consider starting loperamide 2 mg 1–2 times daily as secondary prophylaxis (i.e., use of loperamide to prevent further diarrhea).

**Table 5 Dose Modification Guidelines for Treatment-Related Non-Hematologic Toxicities (cont.)**

Toxicity	Palbociclib and/or GDC-0810 Dose Modification
Nausea and or Vomiting:	
General and Grade 1	See Section 10.4.1.
Grade $\geq 2$ nausea or vomiting	

If persistent despite maximal medical therapy, withhold GDC-0810 until recovery to Grade <math>\leq 1</math>. If no improvement is noted in palbociclib combination patient, consider additionally withholding palbociclib until recovery to Grade <math>\leq 1</math>.

Grade $\geq 3$ nausea or vomiting	

Manage with anti-emetics and supportive care.

Withhold GDC-0810 and/or palbociclib until symptoms resolve to Grade <math>\leq 1</math>.

On resolution of first occurrence, reduce dose of GDC-0810 by one dose level when treatment resumes and consider reducing dose of palbociclib.

On resolution of second occurrence, reduce dose of GDC-0810 and/or palbociclib by one dose level when treatment resumes.

Venous thromboembolic events (including pulmonary embolism):	
General and Grade 1–2	See Section 10.4.1.
Grade $\geq 3$ venous thromboembolic events (including pulmonary embolism)	

Withhold GDC-0810 and palbociclib until patient is stable and consult with Sponsor before resuming treatment.

Vaginal hemorrhage:	
General and Grade 1	See Section 10.4.1.
Grade $\geq 2$ vaginal hemorrhage	

Withhold GDC-0810 and palbociclib until Grade <math>\leq 1</math> and consult with Sponsor before resuming treatment.

Grade $\geq 3$ non-hematologic toxicity	

Withhold GDC-0810 and/or palbociclib until symptoms resolve to Grade <math>\leq 1</math> or Grade <math>\leq 2</math> (after discussion with Medical Monitor).

If repeated toxicity is seen in the next cycle or if recovery from Grade 3 is delayed beyond 7 days discuss with Medical Monitor.

**Table 5 Dose Modification Guidelines for Treatment-Related Non-Hematologic Toxicities (cont.)**

Toxicity	Palbociclib and/or GDC-0810 Dose Modification
Elevation of hepatic transaminases:	
General	

• Patients presenting with jaundice, coagulopathy, abdominal pain, or other symptoms suggestive of hepatic pathology should have their liver function tests checked and imaging of the liver performed. If the liver enzymes are elevated with no obvious malignant cause found, a hepatologist should be consulted.

• Patients experiencing hepatic enzyme elevation should be treated and managed per standard of care.

Grade $\geq 3$	

• Hold study drug until resolution to baseline or below upper limit of normal (ULN).

**Table 6 Dose Modification Guidelines for Hematologic Toxicities**

Toxicity	Palbociclib	GDC-0810
Neutropenia or thrombocytopenia Grade $\leq 2$	No dose modification required.	No dose modification required.
Uncomplicated Grade 3 neutropenia	Withhold palbociclib until recovery to Grade $\leq 2$ ( $\geq 1000/\text{mm}^3$ ). No dose adjustment is required unless recovery of neutrophil count is delayed a,b , in which case reduce by one dose level.	No dose modification required.
Uncomplicated Grade 4 neutropenia (ANC $< 500/\text{mm}^3$ )	Withhold palbociclib until recovery to Grade $\leq 2$ ( $\geq 1000/\text{mm}^3$ ). Resume at next lower dose. Reduce by two dose levels c if neutrophil recovery is delayed a or in case of recurrent Grade 4 event.	No dose modification required.
Grade $\geq 3$ neutropenia associated with infection or fever	Withhold palbociclib until neutrophil count recovery to Grade $\leq 2$ ( $\geq 1000/\text{mm}^3$ ) and afebrile and infection is clinically improving. Resume palbociclib at next lower dose. Reduce by two dose levels c if neutrophil recovery is delayed a . In case of Grade 4 febrile neutropenia, discuss with Medical Monitor prior to resuming palbociclib.	No dose modification required.
Uncomplicated Grade $\geq 3$ thrombocytopenia (platelet count $< 50,000/\text{mm}^3$ )	Withhold palbociclib until recovery to Grade $\leq 2$ ( $\geq 50,000/\text{mm}^3$ ). Resume at next lower dose. Reduce by two dose levels c if platelet count recovery is delayed a or in case of recurrent Grade 4 event.	No dose modification required.

ANC=absolute neutrophil count.

a If recovery of neutrophils to  $\geq 1000/\text{mm}^3$  or platelet count to  $\geq 50,000/\text{mm}^3$  takes  $> 2$  weeks (including dose holding due to toxicity, the scheduled week off treatment, or  $> 7$  days of cycle delay).

b If uncomplicated Grade 3 neutropenia recurs in 2 consecutive cycles, after recovery as per retreatment criteria (ANC  $\geq 1000/\text{mm}^3$  and no fever), treatment may restart at the next lower dose level at investigator's discretion.

c If no further dose reduction is possible (i.e. patient is already receiving 75 mg/day according to the 3/1 schedule), consider changing the schedule to 75 mg/day, 2 weeks on/2 weeks off, or discontinue palbociclib and continue with GDC-0810 alone.

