**Table 2 Combination Cohorts (Phase Ib)**

Phase	Stage	Dose and Schedule	Cohorts
Ib	Dose Escalation	400 mg GDC-0810 (28/0) + 100 mg Palbociclib (21/7)	C0 b
Ib	Dose Escalation	400 mg GDC-0810 (28/0) + 125 mg Palbociclib (21/7)	C1
Ib	Dose Escalation	600 mg GDC-0810 (28/0) + 125 mg Palbociclib (21/7)	C2
Ib	Dose Expansion	GDC-0810 (28/0) at RP3D + 125 mg Palbociclib (21/7)	C3 a
Ib	Safety Run-in	≤600 mg GDC-0810 (28/0) + LHRH agonist (Q4W)	D1
Ib	Dose Expansion	≤600 mg GDC-0810 (28/0) + LHRH agonist (Q4W)	D2

28/0=Days 1–28 of 28-day cycle (no dosing holiday); 21/7=Days 1–21 of 28-day cycle (no dosing holiday); LHRH=luteinizing hormone releasing hormone; Q4W=every 4 weeks.

a Up to 6 peri- or premenopausal women may be enrolled in Cohort C3 to receive a combination of GDC-0810 (28/0), LHRH (Q4W), and palbociclib (21/7).

b Potential de-escalation cohort

These doses are guidelines only; actual dose escalations or reductions (including different regimens, e.g. 2 weeks on/2 weeks off schedule for palbociclib) may differ and will be determined jointly by Sponsor and study investigators during meetings at which all available safety and PK data will be reviewed prior to dose escalation decisions.

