## **10.4 DOSE MODIFICATIONS**

Patients who have had treatment interruptions due to reasons other than DLTs may restart daily dosing at the same dose at the discretion of the investigator when the toxicity has resolved to Grade  $\leq 1$  or baseline; however, any patients whose treatment is interrupted for an adverse event that is related to study drug and who do not restart treatment within 28 days will be withdrawn from study treatment.

For patients experiencing a DLT, treatment should be held until the severity of the toxicity decreases to Grade  $\leq 1$  or baseline. If they are deriving clinical benefit, patients may be restarted on study drug at the next lower dose level that has been tested in a previous cohort, at the discretion of the investigator and in consultation with the Sponsor. For Phase Ia and Phase IIa, no more than 2 dose reductions of GDC-0810 will be allowed.

For Phase Ib Cohort C1 a maximum of two dose reductions of GDC-0810 and palbociclib will be allowed. No dose reductions are planned for the LHRH agonists (Cohort D1). GDC-0810 dose reductions should be managed without changing regimen, for example, patients in Phase Ia who were being treated on a BID regimen will dose reduce to the next lower GDC-0810 dose level but still administered as BID. Similarly, Phase Ia patients who were being treated without a fasting requirement will dose reduce to the next lower dose level but still administered without a fasting requirement.

Doses reduced for drug-related toxicity should generally not be re-escalated. However, intrapatient re-escalation back to the previous dose level may be permitted at the discretion of the investigator and in consultation with the Sponsor.

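### Table 6's two-level palbociclib reduction cannot be carried out from 100 mg if counted from the current dose, and footnote c does not cover that patient

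*Combined protocol and SAP*

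**What the plan says.** Table 2 starts palbociclib at 125 mg in Cohort C1 ("400 mg GDC-0810 (28/0) + 125 mg Palbociclib (21/7") and at 100 mg in the potential de-escalation Cohort C0 ("400 mg GDC-0810 (28/0) + 100 mg Palbociclib (21/7").

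Section 10.4.2 sets the step ("Palbociclib dose reductions may occur in decrements of 25 mg") and the ladder ("the possible palbociclib doses permitted in Phase Ib Cohorts C1, C2 and C3 are 125 mg, 100 mg, and 75 mg"). It also sets the floor: "Palbociclib dose de-escalation below 75 mg/day is not allowed". The same sentence goes on to allow a change of schedule in consultation with the sponsor, with 75 mg/day two weeks on and two weeks off as the example. Section 7.3 repeats the floor and the schedule option, there in consultation with the Medical Monitor. Section 10.4 limits the number of steps for Cohort C1: "a maximum of two dose reductions of GDC-0810 and palbociclib will be allowed".

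For uncomplicated Grade 4 neutropenia, uncomplicated Grade ≥3 thrombocytopenia and Grade 4 anaemia, Table 6 says, after withholding until recovery, "Resume at next lower dose. Reduce by two dose levels". The two-level step applies if recovery is delayed (more than 2 weeks, footnote a) or if a Grade 4 event recurs. Two further rows, neutropenia with infection or fever and thrombocytopenia with bleeding, contain the two-level step for delayed recovery only.

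Footnote c is attached to the two-level wording in all five rows. It begins "If no further dose reduction is possible (i.e. patient is already receiving 75 mg/day according to the 3/1 schedule" and then offers the two-weeks-on, two-weeks-off schedule, or stopping palbociclib and continuing GDC-0810 alone.

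**The concern.** The ladder has three rungs, so a two-level step is available only from the top one. Yet a first Grade 4 event normally moves a Cohort C1 patient off the top rung. When the two-level rule is triggered by recurrence, the patient will usually be at 100 mg, with one level left rather than two. Table 6 and the floor then cannot both be followed, and the footnote meant for patients who have run out of levels describes a different patient.

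The setting is severe cytopenia, where a site needs one clear instruction. Version 9 lets combination patients with benefit stay on treatment, requires hematology at least monthly for them, and states that the dose modification guidelines were updated. The Grade 4 anaemia row is in italics, which the amendment rationale uses to mark substantive new text, so the two-level wording appears to have been extended to a new row in this version. The trigger is foreseeable: Section 2.2 reports Grade 4 neutropenia in 6% of patients on palbociclib plus letrozole, although it gives no rate of recurrence.

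If sites resolve the gap differently, patients with the same toxicity will be handled differently, and palbociclib exposure after toxicity will be hard to interpret in a very small cohort.

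**Working it through.** **Inputs.** Starting dose 125 mg (C1) or 100 mg (C0), from Table 2. Step 25 mg and floor 75 mg/day, from Section 10.4.2 (floor also in Section 7.3). At most two reductions, from Section 10.4.

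**Reproducing the ladder.** Dose after k levels = start − 25k. From 125 mg, k = 0, 1, 2 gives 125, 100 and 75 mg. This matches Section 10.4.2, and the lowest rung equals the floor.

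**Two levels counted from the current dose** (dose − 2 × 25 = dose − 50):

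| Situation | Dose when triggered | Result | At or above 75 mg? | Footnote c condition met? |
|---|---|---|---|---|
| C1, first event, delayed recovery | 125 mg | 75 mg | yes | not needed |
| C1, first Grade 4 event without delay (125 − 25 = 100), then recurrent Grade 4 | 100 mg | 50 mg | no, 25 mg short | no |
| C1, already reduced to 100 mg for another toxicity, then an event with delayed recovery | 100 mg | 50 mg | no | no |
| C1, still at or back at 125 mg, recurrent Grade 4 | 125 mg | 75 mg | yes | not needed |
| C1, at 75 mg, recurrent Grade 4 | 75 mg | 25 mg | no | yes |
| C0, first event, delayed recovery | 100 mg | 50 mg | no | no |
| C0, first event without delay (100 − 25 = 75), then recurrent Grade 4 | 75 mg | 25 mg | no | yes |

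Every case left without an instruction is a patient at 100 mg. Besides a first Grade 4 event, routes to 100 mg in C1 include delayed recovery from Grade 3 neutropenia or Grade 3 anaemia (one level, Table 6) and Grade ≥3 diarrhea, for which Table 5 asks sites to consider reducing palbociclib.

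**Two levels counted in total from the starting dose.** C1: 125 − 50 = 75 mg, permitted. C0: 100 − 50 = 50 mg, below the floor.

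**Rows affected.** Recurrent Grade 4 is a trigger in three rows. Delayed recovery is a trigger in all five, and causes the conflict only if the patient is already at 100 mg.

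**The limit of two reductions.** One level at the first event and two at recurrence make three levels, whereas the ladder has room for two. Section 10.4, however, counts reductions rather than levels. If a two-level step is one reduction, the total is 1 + 1 = 2, within the limit; if it is two, the total is 1 + 2 = 3, over it. The documents do not say which.

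**Spread of readings for a patient at 100 mg.** The current cycle total is 100 × 21 = 2100 mg. One level down on the same schedule gives 75 × 21 = 1575 mg. The alternative schedule gives 75 × 14 = 1050 mg. Stopping gives 0 mg. The literal 50 mg would give 50 × 21 = 1050 mg but is prohibited. These totals show how far sites could diverge; none is put forward as correct.

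**The case against.** The best counter-argument is that Table 6 never says where the two levels start. Counted in total from 125 mg, they end at 75 mg: on the ladder, at the floor, and followed naturally by footnote c for anyone already there. The text does not exclude that reading, and for a C1 patient it removes the conflict. It is not the natural reading, though. The next lower dose is relative to the current dose, and footnote c speaks of a further reduction for a patient already receiving a given dose. Table 5 lowers GDC-0810 by one level at a first and again at a second occurrence, which works only from the current dose. The starting-dose reading also fails for a C0 patient. The result is an ambiguity that sites should not have to resolve.

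Other points stand and narrow the concern:

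- A recurrence need not find the patient at 100 mg. Section 10.4 permits re-escalation. Section 10.4.2 bars dose modification during the DLT evaluation period, so a patient whose first event fell in Cycle 1 and who resumed within it could still be at 125 mg.
- Footnote c is not the only way out. The schedule change in Sections 7.3 and 10.4.2 is not restricted to patients at 75 mg, and Table 6 sends Grade 4 febrile neutropenia and Grade 4 thrombocytopenia with bleeding to the Medical Monitor. But the schedule change names no action for 100 mg, and the three rows with the recurrence trigger require no such discussion.
- The C0 path may be theoretical, since Section 10.2.3 says no patients will be enrolled in C0.

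A reader might infer that the protocol orders a 50 mg dose. It does not. The prohibition below 75 mg is explicit, Table 6 is a set of guidelines, and footnote c shows that its authors had the floor in mind. Nor do the documents support the view that a patient at 75 mg is left without guidance, or that the two-reduction limit is necessarily breached.

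**Conclusion.** The point holds in a limited form. If the levels are counted from the current dose, the two-level instruction cannot be carried out for a patient at 100 mg: it falls 25 mg below the floor, and footnote c does not apply. This arises at a recurrent Grade 4 event in three rows, and at delayed recovery in all five when the patient is already at 100 mg. It does not arise with counting from a 125 mg start, or for a patient at 125 mg or 75 mg.

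The reach is small. Section 1.1 reports 4 patients in Cohort C1 as of 9 September 2016, Section 15.2.3 gives about 5 in C0 and C1 together, and enrollment is closed. The documents do not say how many remain on palbociclib or have been reduced to 100 mg. Because the analyses are descriptive, no formal inference is at risk. The case for acting is that a safety rule still in use conflicts with the protocol's own floor for a foreseeable patient, and that correcting the wording costs almost nothing.

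**What to change.** Reconcile the five two-level rows of Table 6 and footnote c with the 75 mg/day floor (Sections 7.3 and 10.4.2) and the limit of two reductions (Section 10.4). The revised text should state:

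1. whether the levels are counted from the starting dose or the current dose;
2. whether a two-level step uses one or both of the allowed reductions;
3. which instruction governs when two levels are not available, so that a patient at 125, 100 or 75 mg has one unambiguous entry for delayed recovery and, where the row has it, for a recurrent Grade 4 event;
4. whether the consultation in Sections 7.3 and 10.4.2 is required in that situation, and with whom, since one names the Medical Monitor and the other the sponsor.

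The sponsor's clinical team decides the action; no dose or rule is proposed here. The cost is table and footnote wording in an amendment or clarification letter, with no added visits or tests.

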**Table 6 Dose Modification Guidelines for Hematologic Toxicities (cont.)**

Toxicity	Palbociclib	GDC-0810
Grade $\geq 3$ thrombocytopenia (platelet count $<50,000/\text{mm}^3$ ) associated with bleeding	
Withhold palbociclib until platelet count recovery to Grade <math>\leq 2</math> (<math>\geq 50,000/\text{mm}^3</math>) and clinically stable.
 
Resume palbociclib at next lower dose. Reduce by two dose levelsc if platelet count recovery is delayeda. In case of recurrent Grade 3 event following a previous delayed recovery of platelet count, discuss with Medical Monitor.
 
In case of Grade 4 thrombocytopenia associated with bleeding, discuss with Medical Monitor prior to resuming palbociclib.
	No dose modification required.
Grade 3 anaemia	Withhold palbociclib until recovery to Grade <math>\leq 2</math> (<math>\geq 8.0 \text{ g/dL}</math>). No dose adjustment is required unless recovery of hemoglobin is delayeda, in which case reduce by one dose level.	No dose modification required.
Grade 4 anaemia	Withhold palbociclib until recovery to Grade <math>\leq 2</math> (<math>\geq 8.0 \text{ g/dL}</math>). Resume at next lower dose. Reduce by two dose levelsc if hemoglobin recovery is delayeda or in case of recurrent Grade 4 event.	No dose modification required.

ANC=absolute neutrophil count.

- a If recovery of neutrophils to  $\geq 1000/\text{mm}^3$  or , platelet count to  $\geq 50,000/\text{mm}^3$ , or hemoglobin to  $\geq 8.0 \text{ g/dL}$  takes  $>2$  weeks (including dose holding due to toxicity, the scheduled week off treatment, or  $>7$  days of cycle delay).
- b If uncomplicated Grade 3 neutropenia recurs in 2 consecutive cycles, after recovery as per retreatment criteria (ANC  $\geq 1000/\text{mm}^3$  and no fever), treatment may restart at the next lower dose level at investigator's discretion.
- c If no further dose reduction is possible (i.e. patient is already receiving 75 mg/day according to the 3/1 schedule), consider changing the schedule to 75 mg/day, 2 weeks on/2 weeks off, or discontinue palbociclib and continue with GDC-0810 alone.

